- Effects on liver: Daily IV doses of G1T28 in rats at  $\geq 10$  mg/kg/day ( $\geq 60$  mg/m^2/day) and in dogs at  $\geq 15$  mg/kg/day (approximately 300 mg/m^2/day) resulted in slightly increased alanine aminotransferase (ALT) and/or aspartate aminotransferase (AST) levels. Liver-related effects in both species were reversible within 2 weeks after the last dose. There were no effects on liver in rats given daily oral doses for 14 days at up to 30 mg/kg (180 mg/m^2).
- Local irritation at the infusion site: Dogs given daily doses of G1T28 for 7 days had occasional episodes of swelling/edema at the infusion site. This was considered likely to be due to leakage or accidental injection of dosing solution into the perivenous tissue.

Although G1T28 induced micronucleus formation in human lymphocytes exposed in vitro, G1T28 is not considered to pose a hazard to human patients, as G1T28 was negative for mutagenic potential in a Good Laboratory Practice (GLP) (and non-GLP) Ames assay, and did not induce phosphorylated histone H2AX ( $\gamma$ H2AX) formation in primary human fibroblasts. In the present study, G1T28 will be administered in conjunction with etoposide/carboplatin, which presents a genotoxic hazard to human subjects. In this context, any slight additional genotoxic hazard posed by G1T28 is negligible.

In female rats, daily administration of G1T28 for 7 days resulted in lower ovary and uterus weights and more rats in metestrus/diestrus, and these effects were reversible within 2 weeks after the last dose. These findings in rats raise the possibility that G1T28 may affect menstrual cycling in women; however, no studies have been done specifically to evaluate the effects of G1T28 on fertility in animals of either sex. For men, studies in rats and dogs do not suggest any potential for impairment of fertility; specifically, there were no pathologic findings in reproductive organs of male rats or dogs given daily doses of G1T28 for 7 days. Nevertheless, patients who are pregnant or lactating should not receive G1T28. Heterosexual couples in which the female is of childbearing potential must use appropriate birth control methods.

The nonclinical package as a whole indicates that rats and dogs were appropriate species for evaluating the toxicity of G1T28. In both species, the toxicity profile was similar.

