#### 11.3.1.7. Documentation of Adverse Events and Serious Adverse Events

All AEs will be documented in the appropriate section of the eCRF. The CTCAE, Version 4.03 grading scale referenced in [Appendix 1](#) is provided to assist in categorizing and grading AEs. All SAEs (see Section [11.3.1.2](#)) will be additionally documented on the SAE report form. For AEs occurring while the patient is in the clinic setting, ie, before, during, or after study drug administration, the start time and stop time of the AE should be recorded in the source document.

The following will be recorded for each AE in the eCRF:

- A description of the AE in medical terms, not as reported by the patient. Whenever possible, a diagnosis should be given when signs and symptoms are due to common etiology (eg, cough, runny nose, sneezing, sore throat, and head congestion should be reported as “upper respiratory infection”).
- Date of onset (start date)
- Date of recovery (stop date)
- Grade as assessed by the investigator according to the definitions in the AE Grading Scale. If the AE is not specifically listed in [Appendix 1](#), use the following grades:
  - Grade 1 mild
  - Grade 2 moderate
  - Grade 3 severe
  - Grade 4 life-threatening or disabling
  - Grade 5 death

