### 13.5.2. **Methods of Analysis for Safety Endpoints**

The safety analysis will be performed in all patients who have received at least 1 dose of study drug. Adverse event data will be coded to system organ class and preferred term using MedDRA (Version 17.1, or later). Treatment emergence is defined as any AE occurring on or after the day of first dose through the Post-Treatment Visit. The number and percentage of patients experiencing any treatment-emergent AE overall and by system organ class and preferred term will be tabulated. The incidence rates by cycle and adjusted by exposure time will also be presented. Each AE will be counted only once for a given patient at each level of summarization. In analyses of grade and causality, if the same AE occurs on multiple occasions, the highest grade and strongest relationship to study drug will be assumed. Infusion-related reactions will be tabulated separately from the AEs.

Absolute values and changes from baseline in vital signs, ECG readings, and hematology and clinical chemistry parameters will be tabulated at each visit during the Treatment Phase. Toxicities for clinical labs will be characterized according to the CTCAE, Version 4.03. Shifts in toxicity grades from baseline to each visit will be summarized.

Overall disease responses as determined by RECIST, Version 1.1 will be summarized by response level at each visit and best overall response. The number of patients with a confirmed objective disease response, defined as patients with a best overall response of confirmed CR or PR obtained during the Treatment Phase, will be summarized.

Progression-free survival is measured from date of first dose date until date of documented disease progression or death and will be estimated using the Kaplan-Meier method. Patients who have not died or had documented disease progression at the time of analysis will be censored on the last onstudy date with nonmissing tumor response data.

Overall survival is measured from date of enrollment until death and will be estimated using the Kaplan-Meier method. Patients alive at the time of analysis will be censored on the last date the patient was known to be alive.

Censoring techniques that account for missing tumor assessments and potential differences in the duration of time patient has onstudy tumor assessments may be applied for PFS data. The methods will be described in the SAP.

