5.2. Safety Endpoints

5.2.1. Adverse Events (AEs)

All AEs will be coded from verbatim text to PTs and grouped by SOC using the MedDRA Version 20.1. AEs will be collected from the time of signature of informed consent throughout the treatment period and including the post-treatment visit. AEs are graded by investigator according to CTCAE, Version 4.03.

Any AE that started on or after the first dose of study drugs and up to the last dose +30 days will be included as a treatment-emergent AE (TEAE). AEs with an unknown/not reported onset date will also be included.

Other AE variables include drug-related AEs, AEs leading to study drug discontinuation or study withdrawal, AEs leading to death, SAEs.

AEs with onset/end dates that are partially/completely missing will be imputed as follows:

(i) For onset date:

- If only the day part of the AE onset date is missing and occurs in the same month and year as the first dose date of study drug, the date of first dose of study drug will be used as the onset date of the AE. Otherwise, the first day of the month will be used to complete the onset date of the AE;
- If the day and month parts of the AE onset date are missing and occur in the same year as the first dose of study drug, the date of the first dose of study drug will be used as the onset date of the AE. Otherwise, January 1st will be used to complete the onset date of the AE;
- If the AE onset date is completely missing, the date of the first dose of study drug will be used as the onset date of the AE.

(ii) For end date:

- If only the day part of the AE end date is missing, the last day of the month will be used to complete the end date of the AE;
- If the day and month parts of the AE end date are missing, December 31st will be used to complete the end date of the AE;
- If the AE end date is completely missing and the onset date of the AE occurs after the date of the first dose of study drug, the last date during the treatment period +30 days will be used as the AE end date. If the AE end date is completely missing and the onset date of the AE occurs prior to the date of the first dose of study drug the date of the first dose of study drug will be used as the AE end date.

AEs related to hematologic toxicity will be pooled based on the preferred MedDRA Version 20.1. [Table 10](#) outlines those terms that will be consolidated.

Table 10 Preferred Terms to Be Consolidated

Presented term in the table	Preferred Term
Neutropenia	Neutropenia

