	Febrile neutropenia
	Neutrophil count decreased
Anaemia	Anaemia
	Anaemia macrocytic
	Red blood cell count decreased
	Hemoglobin decreased
Thrombocytopenia	Thrombocytopenia
	Platelet count decreased
Lymphopenia	Lymphopenia
	Lymphocyte count decreased
Leukopenia	Leukopenia
	White blood cell count decreased

AEs potentially related to infusion reactions will be pooled based on the PTs of MedDRA Version 20.1. The events described by the PTs listed below that have a start date on the same

date study drug is administered will be summarized and presented in order of decreasing frequency: angioedema, back pain, bronchospasm, wheezing, chest pain, non-cardiac chest pain, hyperhidrosis, malignant dysphagia, dysphagia, oedema, swelling face, flushing, dysphonia, hypotension, hypoxia, paraesthesia oral, pain, phlebitis, pruritic, pyrexia, rash, dermatitis allergic, drug eruption, infusion site rash, injection site rash, rash pruritic, erythema, infusion site erythema, injection site erythema, chills, dyspnoea, syncope, tachycardia, throat tightness, injection site ulcer and mucocutaneous ulceration.

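### The infusion-reaction table has no preferred term for a reaction recorded as a diagnosis (infusion related reaction, hypersensitivity, anaphylactic reaction, urticaria) and appears to count listed symptoms whose onset date was imputed to the first dosing date

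*SAP*

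**What the plan says.** Infusion-related reactions are a named safety endpoint in Protocol 13.5.1, and Protocol 13.5.2 gives them their own display: "Infusion-related reactions will be tabulated separately from the AEs".

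SAP 5.2.1 supplies the operational rule: "AEs potentially related to infusion reactions will be pooled based on the PTs of MedDRA". The list opens with "angioedema, back pain, bronchospasm, wheezing, chest pain, non-cardiac chest pain, hyperhidrosis, malignant dysphagia, dysphagia, oedema, swelling face, flushing" and closes with "chills, dyspnoea, syncope, tachycardia, throat tightness, injection site ulcer and mucocutaneous ulceration". An event qualifies if its PT is on the list and its start date is a day of study drug administration; such events on the same "date study drug is administered will be summarized and presented in order of decreasing frequency". There is no clock-time test against the infusion. SAP 6.2.8.1 refers back to 5.2.1 for the criteria.

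On recording, Protocol 11.3.1.7 says that, whenever possible, "a diagnosis should be given when signs and symptoms are due to common etiology". Protocol 8.4.4.2.1 has a subsection on hypersensitivity reactions graded mild, moderate and severe. It gives generalized urticaria as a severe sign and requires the severe form to be reported as an AE.

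On dates, SAP 5.2.1 says that for an onset with only the day missing, in the first-dose month and year, "the date of first dose of study drug will be used as the onset date of the AE". Onsets with day and month missing in the first-dose year, and onsets missing completely, are treated the same way. SAP 6.1.2 says that imputed dates serve to determine each AE's status and makes no exception for infusion reactions.

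**The concern.** The site instruction and the analysis filter pull in different directions. The protocol asks for one diagnosis in place of several symptoms. The SAP filter recognises symptoms and some specific reaction terms, but not the general diagnoses under which an infusion or allergic reaction would naturally be coded. A same-day reaction could then count or not count depending on how the site worded it.

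The date rule can act the other way. Dyspnoea, chest pain or back pain with an incomplete onset date can be assigned to Cycle 1 Day 1, which is a dosing date, and so meet the same-day criterion with no recorded evidence of same-day onset.

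At stake is the reported incidence of one named safety endpoint for an intravenous drug, in a study with safety and tolerability as a primary objective in every part.

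**Working it through.** The documents state no figure for this endpoint, so there is none to reproduce. The checks are a term search, a comparison of sections, and a trace of the date rule.

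**1. Term search.** SAP 5.2.1 lists 36 PTs. Terms containing *infusion related*: 0. *Hypersens-*: 0. *Anaphyl-*: 0. *Urticaria*: 0. The list is not purely symptoms: it includes angioedema, bronchospasm, phlebitis, dermatitis allergic, drug eruption, infusion site rash and erythema, and injection site rash, erythema and ulcer.

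**2. Other routes into the table.** SAP 6.2.8.1 points back to 5.2.1 and adds none.

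**3. One reaction recorded two ways.** Suppose a patient has flushing, wheezing and hypotension on a dosing day.
- Recorded as three symptoms: all three PTs are listed, so the patient is counted.
- Recorded as hypersensitivity, in line with Protocol 11.3.1.7: the PT is not listed, so the patient is not counted.

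**4. Date rule.** Take an arbitrary first dose on 10 March 2017, with six undelayed 21-day cycles and dosing on Days 1 to 3. Applying SAP 5.2.1:

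| Recorded onset | Imputed onset | Dosing date? |
|---|---|---|
| completely missing | 10 Mar 2017 | yes |
| 2017 | 10 Mar 2017 | yes |
| Mar 2017 | 10 Mar 2017 | yes |
| Feb 2017 | 1 Feb 2017 | no |
| May 2017 | 1 May 2017 | no |
| 2016 | 1 Jan 2016 | no |

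The first three rows always land on the first dosing date, so a listed PT is counted every time. For a month-only onset in a later month, the imputed date is the first of that month. Over every first-dose date in one calendar year, with the same undelayed schedule, that date fell on a dosing day in 204 of 1460 cases: 204/1460 = 14.0%.

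**5. Comparison with a fully dated, unrelated symptom.** Dosing days are 3 of 21, and 3/21 = 14.3%, or about 1 in 7. If onset is spread evenly over the cycle, that is the chance that an unrelated listed symptom qualifies. Under the first three rows the chance is 100%, seven times as high.

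**6. Scale.** With 70 patients randomized 1:1, 70/2 = 35 per arm and 1/35 = 2.9 percentage points per misclassified patient. This says how much one patient matters. It does not estimate how many are affected.

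**The case against.** The strongest defence is that this is a deliberately broad screen. The SAP calls the events only potentially related to infusion reactions and ranks them by frequency, so a reader can see back pain for what it is. A reaction recorded as a diagnosis is not lost to the report: SAP 6.2.8.1 shows it by SOC and PT, by grade and by relationship to each drug, as an SAE or an AE leading to discontinuation where applicable, and in listings. SAP 6.2.8 plans no inferential safety analysis. The list may have been drawn up from blinded study terms, in which case the absent diagnoses may simply not have occurred; the documents do not say.

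On dates, no sentence says that imputed onsets feed this filter. Onset date is an eCRF item, and Protocol 11.3.1.1 excludes pre-existing conditions that do not worsen, which keeps out many baseline lung-cancer symptoms. The rate of incomplete onset dates is not given.

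These points limit the consequence. They do not remove the gap: the dedicated table still has no place for the general reaction diagnoses, and nothing exempts it from imputation.

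A reader might infer more than the documents support:
- *That sites are told to report the four missing terms.* Protocol 11.3.1.7 is a general rule with a respiratory-infection example. Anaphylaxis is not mentioned, urticaria appears as a sign, and the hypersensitivity text sits under etoposide and carboplatin dose modification.
- *That infusion-site swelling is an expected risk that the list must carry.* Protocol 4.3.4 reports that dogs "had occasional episodes of swelling/edema at the infusion site" and considers leakage or perivenous injection the likely cause. Adding site-swelling or extravasation terms, or dropping malignant dysphagia, is a matter of preference.

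**Conclusion.** The point holds as a gap in one descriptive safety table. The term gap follows directly from the text: 0 of 36 PTs cover infusion related reaction, hypersensitivity, anaphylactic reaction or urticaria, and there is no second route. The imputation point rests on reading SAP 5.2.1 and 6.1.2 together, because their use for this table is implied rather than stated.

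The number of events affected cannot be computed, since the documents give neither the rate of reactions recorded as diagnoses nor the rate of incomplete onset dates. It would be tempting to conclude that the table understates reactions or dilutes a difference from placebo. The documents do not support either conclusion: omissions lower the count, imputed inclusions raise it, the net direction is unknown, and no between-arm test of this endpoint is planned. Sample size, power and significance levels are untouched. The change is still worth making, because the dedicated table is where a reader will look for this endpoint's incidence.

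**What to change.** Amend SAP 5.2.1 before unblinding:

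- Add the PTs infusion related reaction, hypersensitivity and drug hypersensitivity, anaphylactic reaction and anaphylactic shock, and urticaria.
- State that only events with a recorded, not imputed, onset date on a dosing day enter the table.
- Put events with a qualifying PT and an imputed onset date in a separate listing.

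The cost is a few lines of SAP text, a changed PT and date filter, and one short listing. The small downside is that a true symptom-level reaction with an incomplete date appears only in that listing.

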5.2.2. Vital Signs

Vital signs include pulse rate, respiratory rate, systolic blood pressure (SBP), diastolic blood pressure (DBP), weight, height (only measured at screening), and body temperature. Body Mass Index (BMI) will be computed as $\text{weight (kg)}/[\text{height (m)}]^2$, BSA will be computed using DuBois-DuBois formula as $0.20247 \times [\text{height (m)}]^{0.725} \times [\text{weight (kg)}]^{0.425}$.

For vital signs, change from baseline to each post-baseline visit and timepoint will be calculated. Vitals will be summarized by visit as collected and not windowed.

The potentially clinically significant findings of vital signs will also be defined based on criteria defined in [Table 11](#):

Table 11 Potentially Clinically Significant Criteria for Vital Signs

Vital Sign Parameter	Criterion value	Change from baseline
SBP	≥ 180 mmHg	Increase ≥ 40 mmHg
	≤ 90 mmHg	Decrease ≥ 40 mmHg
DBP	≥ 105 mmHg	Increase ≥ 20 mmHg
	≤ 50 mmHg	Decrease ≥ 20 mmHg
Pulse	≥ 120 bpm	Increase ≥ 40 bpm
	≤ 50 bpm	Decrease ≥ 40 bpm
Weight	n/a	Change $\geq 10\%$

bpm = beats per minute

5.2.3. Laboratory

Blood and urine samples for the determination of clinical chemistry, hematology, and urinalysis laboratory variables described in [Table 12](#) will be measured.

Table 12 Laboratory Assessment

Lab Category	Lab tests
Hematology	hemoglobin, hematocrit, white blood cell (WBC) with differential, platelet counts, ANC, ALC, Monocyte Absolute, Basophil Absolute, Eosinophil Absolute, and other non-protocol specified tests
Chemistry	albumin, Alkaline Phosphatase (ALP), total bilirubin, calcium, chloride, creatinine, glucose, inorganic phosphorus, potassium, total protein, Alanine Aminotransferase (ALT), Aspartate Aminotransferase (AST), Lactate Dehydrogenase (LDH),

Lab Category	Lab tests
	sodium, and Blood Urea Nitrogen (BUN), and other non-protocol specified tests
Urinalysis	semiquantitative dipstick: specific gravity, pH, evaluation of glucose, protein, bilirubin, ketones, leukocytes, and hemoglobin microscopic examination, including RBC, WBC, and casts will be performed, if necessary

Change from baseline in laboratory test results to each assessment will be calculated; for hematology parameters, the change from cycle baseline will also be obtained. The non-protocol specified tests and urinalysis results will not be summarized; they will only be included in listings.

Clinical laboratory results will be graded according to CTCAE criteria, Version 4.03 which can be found in [Table A-1](#) of Appendix. Any graded abnormality that occurs following the initiation of study drug and represents at least a 1-grade increase from the baseline assessment is defined as treatment emergent. Any assessment for which CTCAE toxicity grades are not available, will not be included in any analyses for which toxicity grades are required.

Analysis of Abnormal Hepatic Laboratory Values

The following categories of abnormal hepatic laboratory values will be evaluated for any occurrence among all post baseline assessments.

- ALT and/or AST >3x ULN, ALP < 2xULN, and Total Bilirubin > 2x ULN
- AST > 3,5,8,10, and 20x ULN, AST >5x ULN for more than 5 weeks
- ALT > 3,5,8,10, and 20x ULN, ALT > 5x ULN for more than 5 weeks
- Total Bilirubin >1.5 or >2x ULN

5.2.4. Electrocardiograms

Electrocardiogram (ECG) parameters include heart rate, PR interval, and QT, QTcB, QTcF and QRS intervals. Change from baseline to each post-baseline visit will be calculated and summarized by visit as collected and not windowed. Visits and timepoints only collected for PK subjects in Part 1 will be listed but not summarized.

Potentially clinically significant ECG findings will be identified using the criteria which are included in [Table 13](#). ECG results are interpreted as normal, abnormal but not clinically significant, or abnormal and clinically significant.

Table 13 Potentially Clinically Significant Criteria for ECG

ECG Parameter	Criterion value
Heart Rate	>120 bpm
	<50 bpm
PR Interval	≥ 210ms
QRS Interval	≥ 120ms
	≤ 50ms
QT Interval	≥ 500ms
	≤ 300ms

ECG Parameter	Criterion value
QTcB, QTcF Intervals	$\geq 500\text{ms}$
	$\geq 480\text{ms}$
	$\geq 450\text{ms}$
	$\leq 300\text{ms}$
	Change from baseline $\geq 30\text{ ms}$
	Change from baseline $\geq 60\text{ ms}$

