#### 4.3.4. Potential Risks

When administered IV daily for 7 days, G1T28 was tolerated in rats at up to 50 mg/kg (approximately 300 mg/m^2) and in dogs at up to 15 mg/kg (approximately 300 mg/m^2), with toxicity characterized chiefly by reduced hematopoiesis that involved all cell lineages and was a reflection of the drug's intended pharmacodynamic activity. The magnitude and/or duration of effect differed among cell lineages, but were dose related in all lineages. Effects on hematopoiesis were readily monitored by peripheral blood cell counts and were reversible when dosing stopped. Clinically significant leukopenia occurred in rats and dogs given IV G1T28 for 7 days at ≥ 150 and 300 mg/m^2, respectively, and it led to morbidity and mortality in dogs given daily doses for 6 days at 900 mg/m^2.

In addition to the intended effects on hematopoiesis, animal studies with G1T28 suggest that potential side effects in human patients might include the following:

- **Pulmonary macrophage accumulation:** In rats, daily oral doses of G1T28 for 14 days at ≥ 5 mg/kg (≥ 30 mg/m^2) resulted in minimal to mild accumulation of foamy macrophages in alveoli. The magnitude of this finding increased with dose level, but it was not associated with any discernable change in the rate or character of respiration. Macrophage accumulation showed evidence of resolving within 3 weeks after dosing stopped. Pulmonary macrophage accumulation was also seen in dogs given daily IV doses of G1T28 by 30-minute infusion at 45 mg/kg (900 mg/m^2) for 5 days, at which point dosing was stopped due to toxicity. The DLT in these dogs was considered to be severe immunocompromise secondary to inhibition of myelopoiesis and lymphopoiesis; ie, an extension of the primary pharmacodynamic activity of G1T28.

- Increased heart rate: In dogs, single IV doses of G1T28 at  $\geq 15$  mg/kg ( $\geq 300$  mg/m^2) produced increases in heart rate that were relatively mild (30 to 60 beats per minute [bpm]) and resolved within a few hours.

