- c Monthly phone calls will be made to each patient that is in the long-term Survival Follow-up Phase. Patients will be followed for survival until at least 50% of the patients in Part 2 have died. Any anticancer therapies used will be collected. In addition, blood samples for hematology and immunologic marker assessment will be collected at  $60 \pm 7$  days after the Post-Treatment Visit for patients in Part 2 only.
- d Informed consent may be obtained up to 28 days prior to the first study treatment administration.
- e Including medical, surgical, radiation history, smoking history, family history, documentation of tumor diagnosis, baseline signs and symptoms within 4 weeks prior to randomization, weight loss in the 6 months prior to randomization ( $\leq 5\%$  or  $> 5\%$ ), and medications taken within 14 days of enrollment.
- f Height will only be measured at the screening visit. Body surface area calculation (based on actual body weight) will be completed on Day 1 of each cycle and vital signs obtained immediately before and after G1T28 or placebo and E/P infusions. Vitals only need to be taken once between infusions.
- g Clinical chemistry will be obtained (albumin, alkaline phosphatase, total bilirubin, calcium, chloride, creatinine, glucose, inorganic phosphorus, potassium, total protein, ALT, AST, lactate dehydrogenase [LDH], sodium, and blood urea nitrogen [BUN]); see Section 11.3.2. Clinical chemistry and urine analysis may be obtained up to 72 hours prior to the first dose of each cycle of G1T28 or placebo + E/P therapy.
- h Hematology will be obtained (hemoglobin, hematocrit, WBCs with differential, and platelet counts); see Section 11.3.2. Hematology may be obtained up to 24 hours prior to first dose of each cycle of G1T28/placebo + EP therapy.
- i In Part 2 only, hematology will be collected at 60 days after the Post-Treatment Visit.
- j Patients participating in the Phase 1b dose-finding portion of Part 1 of the study, who have PK samples obtained, will have ECGs completed at the following time points on Days 1 and 3 of Cycle 1: predose, end of infusion (EOI) of G1T28, 2 hours ( $\pm 10$  minutes) after the start of G1T28, and 6.5 hours ( $\pm 15$  minutes) after the start of G1T28. The 2-hour ECG will be completed once the etoposide infusion is complete.

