### 11.3.5. **Electrocardiogram Assessments**

Standard 12-lead ECGs will be performed as outlined in [Table 9-1](#). Obtain ECGs in the Phase 1b dose-finding portion of Part 1 only if PK samples are also obtained. Patients should rest for 5 minutes prior to each ECG assessment.

The investigator or designee should review the ECGs for any abnormalities as compared with predose ECGs.

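### The SAP lists but does not summarise the study's only scheduled on-drug ECGs, so its by-visit ECG tables cannot show an acute effect on QTc, PR or QRS

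*SAP*

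**What the plan says.** **When ECGs are taken.** Protocol sections 10.1 and 10.6 schedule an ECG for everyone at screening and at the Post-Treatment Visit. Table 9-1, footnote b, places that visit 30 days (+3) after the last dose. During treatment, Table 9-1, footnote j, says that Phase 1b patients who have PK samples "will have ECGs completed at the following time points on Days 1 and 3 of Cycle 1: predose, end of infusion (EOI) of G1T28", then 2 h and 6.5 h after the start of G1T28. Protocol section 11.3.5 repeats the link to PK sampling: "Obtain ECGs in the Phase 1b dose-finding portion of Part 1 only if PK samples are also obtained." Section 10.3 makes these ECGs optional after Cohort 1.

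**What the protocol wants reported.** Section 13.5.1 names ECG readings as a safety endpoint. Section 13.5.2 says that absolute values and changes from baseline "will be tabulated at each visit during the Treatment Phase", with no exception for PK patients. Section 13.2.3 has Part 1 summarised by dose level.

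**What the SAP does.** Section 5.2.4 first sets the general rule: "Change from baseline to each post-baseline visit will be calculated and summarized by visit as collected and not windowed." It then adds: "Visits and timepoints only collected for PK subjects in Part 1 will be listed but not summarized." Section 6.2.8.6 promises descriptive statistics for each ECG parameter and a count of patients who meet a Table 13 criterion during the treatment period. It does not repeat the exclusion. Section 7, which lists analyses dropped from the protocol, does not mention ECGs.

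**The concern.** Safety and tolerability is a primary objective in every part of the study. A reader of the ECG tables will take change from baseline to mean change under treatment. If every scheduled tracing taken under treatment goes to a listing, what remains compares a pre-treatment ECG with one taken about a month after dosing ended. Such a table can look reassuring about conduction and repolarisation when it holds no scheduled on-drug tracing.

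Two things add to this. The protocol's wording calls for the tabulation that the SAP drops, and the SAP does not record the change. The SAP also treats vital signs the other way: section 5.2.2 calculates change to each visit and timepoint. It gives no reason for the difference.

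**Working it through.** The documents give no figure to reproduce here. The check is a cross-reading of the ECG schedule against the summary rule, plus one division.

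**1. Which scheduled ECGs are on drug?**
- Screening: before any dose, all patients.
- Cycle 1 Days 1 and 3: Phase 1b PK patients only. The columns in Table 9-1 are headed as covering every odd cycle, and the ECG footnote letters partly point to the hematology footnote. Protocol sections 10.3 and 11.3.5 settle the intent: these ECGs belong to Cycle 1 of the Phase 1b portion.
- Post-Treatment Visit: all patients, 30 to 33 days after the last dose.

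The expansion cohort and Part 2 therefore have no scheduled on-drug ECG. The set named in SAP section 5.2.4 is the whole of the scheduled on-drug data.

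**2. How far off drug is the remaining post-baseline ECG?**
- Inputs: 30 to 33 days (Table 9-1, footnote b); geometric mean half-life 12.9 to 14.7 h at 48 to 192 mg/m² (Protocol section 4.2).
- Hours: 30 × 24 = 720; 33 × 24 = 792.
- Shortest gap: 720 / 14.7 = 49.0 half-lives.
- Longest gap: 792 / 12.9 = 61.4 half-lives.
- Fraction remaining at the shortest gap: 2^(−49.0) ≈ 2 × 10⁻¹⁵.

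Protocol section 10.6 words the visit as within 30 days (+3), so it could be earlier. Assuming 7 days, 168 / 14.7 = 11.4 half-lives, and the conclusion is the same. The half-life comes from healthy subjects at up to 192 mg/m². If it were three times longer in patients (an assumption), 720 / 44.1 = 16.3 half-lives would still have passed.

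**3. How many tracings are left out of the by-visit tables?**
- Cohort 1: 6 patients × 2 days × 3 tracings after the start of infusion = 36.
- The Day 3 predose tracing follows the Day 2 dose by about a day, under two half-lives. Counting it adds 6, for 42.
- Later Phase 1b cohorts: unknown, because collection is optional.

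**4. What would summarising them give?** The 95% half-width for a mean change at one timepoint is t(0.975, n−1)/√n, in SD units. The one-sided 95% upper bound after zero events is 1 − 0.05^(1/n).

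| n with ECGs | Half-width (SD) | Upper bound, 0 events |
|---|---|---|
| 6 (Cohort 1, assured) | 1.05 | 39% |
| 12 (assumed) | 0.64 | 22% |
| 18 (assumed) | 0.50 | 15% |

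**5. Do the on-drug ECGs enter the Table 13 counts?** The exclusion in section 5.2.4 directly follows the by-visit sentence, and the Table 13 criteria come in a separate paragraph. The Cycle 1 tracings fall inside the treatment period as SAP section 5 defines it. Section 6.2.8.6 is silent. Two programmers could reasonably do it differently.

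**The case against.** The case on the other side has real parts.

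- **Heart rate is assessed elsewhere.** The cardiac signal named in Protocol section 4.3.4 is that single IV doses in dogs "produced increases in heart rate that were relatively mild" and short-lived. Vital signs are taken just before and after infusions on Day 1 of each cycle, in both parts. Tmax is 0.25 to 0.47 h, so the post-infusion pulse falls near peak concentration. SAP Table 11 flags pulse of 120 bpm or more and rises of 40 bpm or more. This stands, and it narrows the gap to QTc, PR and QRS.
- **A drug effect could still be seen.** A reader might infer that the ECG tables can show no drug effect at all. The documents do not support that. The Post-Treatment ECG is taken in both Part 2 arms, so a persistent or late change could appear there against placebo.
- **The Table 13 counts may include these ECGs.** A reader might also infer that no on-drug ECG enters any summary and that the counts will be almost empty. Neither is established. The first depends on the unsettled reading in step 5. The second needs background rates for thresholds such as QTc of 450 ms or more, which can be met off drug and which the documents do not give.
- **There is other evidence and another route.** Phase 1a reported no significant 12-lead ECG changes at up to 192 mg/m². Investigators compare ECGs with predose, and abnormalities needing intervention or further investigation are reported as AEs. Both points are correct. However, the Phase 1a subjects were healthy, Part 2 uses 240 mg/m², and AE reporting does not describe interval changes.
- **The PK analysis is documented separately (SAP section 6.2.10).** It may treat ECGs by timepoint. That document is not available here, so the possibility stays open.
- **The gain is small.** Six patients can be read from a listing, and the main cause is a protocol schedule with no on-drug ECGs beyond Phase 1b. This limits what the fix can deliver. It does not explain why a descriptive study should leave out a descriptive table that its protocol calls for.

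**Conclusion.** The concern holds in a limited form. SAP section 5.2.4 removes the only scheduled on-drug ECGs from the by-visit summaries, contrary to Protocol section 13.5.2 and without an entry in SAP section 7. The remaining post-baseline ECG falls about 49 to 61 half-lives after the last dose, so those tables cannot show an acute on-drug effect on QTc, PR or QRS. At least 36 Cohort 1 tracings are affected. The treatment of the Table 13 counts is an ambiguity and not a proven exclusion.

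This rests on scheduled ECGs only (unscheduled tracings could add data), on Protocol sections 10.3 and 11.3.5 settling the schedule, and on a patient half-life not vastly longer than in healthy subjects. It does not show that a cardiac effect exists: the documents report no QTc, PR or QRS signal. It is a correction worth making, at low cost and with modest yield.

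**What to change.** In SAP sections 5.2.4 and 6.2.8.6:

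1. Delete the sentence that confines the Part 1 PK-patient ECGs to listings.
2. Tabulate the Part 1 Cycle 1 Day 1 and Day 3 ECGs by dose level, day and timepoint, with observed values, change from predose and n in every cell.
3. State that these ECGs enter the Table 13 counts.
4. Label the baseline to Post-Treatment table as an off-drug comparison that does not assess acute effects.

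If the sponsor prefers to keep the exclusion, it should be declared and justified in section 7, and section 6.2.8.6 should say how the Table 13 counts handle these tracings.

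The cost is a few lines of text and one or two extra descriptive tables from data already collected. The downside is limited precision: six uncontrolled patients are assured, starting at 200 mg/m², with later cohorts optional. The tables should carry that caveat. They do not supply on-drug ECG data for the expansion cohort or Part 2.
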